4.2 Exclusion Criteria

All candidates meeting any of the exclusion criteria listed below will be excluded from study participation.

- Younger than 21 years of age
- Care recipient does not have a documented diagnosis of ADRD;
- Self-reports a lack of basic computer skills and no internet access.
- Unable to speak, read, and write English
- Currently attending an ADRD caregiver grief management group
- Experiencing low levels of grief per screening with the Marwit-Meuser Caregiver Grief Inventory-Short Form (scores below 25), and/or experiencing low levels of depressive symptoms per screening with PHQ9 (scores below 10)

4.3 Study Enrollment Procedures

Recruitment. Successful recruitment strategies used in our prior studies²⁵⁻²⁷ will be used. These include: (1) a notice describing the study placed in the providers' monthly newsletters distributed to family caregivers at each facility; (2) study flyers and interest forms posted around the LTCFs (e.g., front desk, family lounge); (3) individualized letters mailed by the facilities' business office introducing the project to family caregivers of ADRD residents; and (4) oral presentations about the project to staff and family caregivers during "family night" events. All written and oral communication will use lay language to describe study purpose, eligibility criteria, intervention, and data collection methods. All written materials will include information about participants' time commitment and study contact information (e-mail address and phone number) that caregivers may use if interested. Interested participants will call or e-mail the study office or fill out the interest form, agreeing to be contacted by study staff. Completed interest forms will be left in the facility's front office or e-mailed directly to the study e-mail address.

Consenting. After they contact the study office, caregivers will be scheduled to undergo eligibility screening. The Project Director will describe the screening process and the instruments used to screen and will ask and document caregivers' verbal consent to be screened for eligibility. Once eligibility is determined, participant caregivers will be

informed of the next steps for enrollment in the study. Study staff will use a Web-based tracking system, Microsoft Access, to document individual reasons for ineligibility and reasons for declining participation in caregivers who met eligibility criteria. Caregivers who meet the inclusion criteria will be sent paper or electronic copies of the study informed consent form for examination. Within the next 24-48 hours, a telephone appointment with the PI or the Project Director will be scheduled to answer any questions caregivers may have about the study prior to obtaining informed consent. If agreeable to join the study and depending on how they preferred to receive the informed consent forms, caregivers will return the signed documents either electronically (e-signature) or in paid, study self-addressed envelopes.

Randomization. The study will be implemented in six waves. Beginning in Month 5 of the study, we will start recruiting and enrolling 24 eligible caregivers for Wave 1, who will be randomly assigned to either the CGMI-V condition ($n = 12$; 6/group) or MT control condition ($n = 12$) using a randomization software for clinical trials. After these 24 caregivers have been enrolled, the study team will start recruiting an additional 24 caregivers for Wave 2. There will be a total of six waves. Each wave will have 8 weeks to recruit, screen, and complete baseline data collection, followed by 8 weeks to implement the intervention condition, and 24 weeks from baseline follow-up. Once enrollment is completed for a wave, recruitment and randomization will start for the following wave. This pattern will be the same for all six waves. This will result in 144 caregivers being enrolled, 72 for the CGMI-V condition, and 72 for the MT control condition (Figure 1).

5 STUDY INTERVENTIONS

5.1 Interventions, Administration, and Duration

The intervention consists of approximately 60-minute sessions delivered weekly for eight consecutive weeks and will follow the standardized CGMI-V intervention manual (Appendix A). The purpose of the CGMI-V is to improve ADRD caregivers' (1) knowledge about late-stage ADRD; (2) communication and conflict resolution skills, and (3) skills managing their loss and chronic grief. Sessions 1-2 address caregiver knowledge about late-stage ADRD, and the resources available to dementia families in the LTCF and the community at large.^{3,28} Sessions 3-4 address caregiver skill in communication and conflict resolution and hands-on care in the context of LTCF.^{3,15-17,28-30} Sessions 5-8 address caregiver loss and grief management skills using discussion guides tailored to specific grief management topics.³¹⁻³⁷ The participant manual outlines each session's content and includes questions to facilitate discussion. Additional materials are provided for knowledge and skill topics. These are fact sheets about late-stage ADRD that are published by the Alzheimer's Association, a guide with resources for ADRD family caregivers published by the Family Caregiver Alliance, and a chapter on hospice services (Appendix A). Table 1 illustrates target areas, session title and content, and resources used in each session.

Table 1. CGMI-V Sessions, Target Areas, Content, and Resources

Session/ Week	Session Title	Target Areas	Content	Resources
1	Getting Started	Knowledge	Address ADRD late and end-stage changes: physical, cognitive, behavioral, emotional	Signs and symptoms of late-stage ADRD Fact Sheet (Alzheimer's Association)
2	What Do You Know About This Place and the Community?	Knowledge	Discuss LTCF philosophy of care, structure, regulations, policies, and personnel roles. Resources for the CG and the CR post placement in the facility and the community at large.	Resources for Persons with Alzheimer Disease; When to Seek Hospice Care (Reynolds, S.)
3	How Do I Get My Message Through?	Communication/Conflict-Resolution Skills	Practice conflict-resolution techniques with LTCF staff, CR, other residents, and their family members	Communication (Alzheimer's Association)
4	Doing for and Working with My Loved One	Hands-on Care Skills	Discuss hands-on care for CR and participation in LTCF activities	Resources and Information Kit-Caregiver Tips (Family Caregiver Alliance)
5	Losses and Separation	Grief Management Skills	Recognize losses and process reaction to separation	Discussion guide in participant manual
6	What Defined Our Relationship?	Grief Management Skills	Recollect and re-experience the relationship with the CR	Discussion guide in participant manual
7	How Do I Let Go and Readjust?	Grief Management Skills	Process relinquishing old attachments and assumptions; process readjusting to the new without forgetting the old	Discussion guide in participant manual
8	Life Goes On	Grief Management Skills	Discuss reinvesting in new attachments, goals; process group closure	Discussion guide in participant manual

ADRD = Alzheimer and related diseases; CG = caregiver; CR = care recipient; LTCF = LTCF facility

Control condition. Caregivers in the control condition will receive Minimal Treatment (MT) consisting of written information about late-stage ADRD (Alzheimer's Association) at baseline. The Project Director will mail caregivers in the MT control condition all written information materials.

5.2 Handling of Study Interventions

CGMI-V is a behavioral group-based intervention delivered by trained interventionists who have group leading experience. The interventionists will receive an eight-hour training on

intervention delivery and technology use (Appendix B).

5.3 Concomitant Interventions

5.3.1 Allowed Interventions

Participants in this group-based study may attend other informal ADRD caregiver support groups.

5.3.2 Required Interventions

There are no concomitant required interventions for this study.

5.3.3 Prohibited Interventions

Participants will be excluded if already attending an ADRD caregiver chronic grief management support group.

5.4 Adherence Assessment:

We will use a Web-based tracking system, Microsoft Access, to assess the receipt of the dose consisting of eight group sessions. We will calculate attendance rates for each participant and record reasons for missing sessions. We will assess enactment of the CGMI-V intervention with specific items in an anonymous participant survey administered at 8 and 24 weeks (e.g., “Since our last assessment meeting, how often have you used: communication skills and conflict resolution techniques learned in the program when interacting with facility staff?”)

6 STUDY PROCEDURES

Study procedures are outlined on the following pages.

6.1 Schedule of Evaluations

Assessment	Eligibility Screening (phone/online interview)	Enrollment /Randomization	Baseline (phone/online interview)	8-weeks post baseline (phone/on line interview)	24-weeks post baseline (phone/on line interview)
Eligibility Screening Verbal Consent	X				
Inclusion/Exclusion Criteria	X				
Study Informed Consent Signed		X			
Caregiver/Care Recipient Socio-demographics			X		
Caregiver/Care Recipient Situational Characteristics			X		
Caregiver Chronic Grief			X	X	X
Caregiver Depressive Symptoms			X	X	X
Caregiver Anxiety Symptoms			X	X	X
Caregiver Positive States of Mind			X	X	X
Conflict with Facility Staff			X	X	X
Satisfaction with Care			X	X	X
Caregiver Knowledge of ADRD			X	X	X
Caregiver Sense of Loss			X	X	X
Caregiver Guilt			X	X	X
Caregiver Role Captivity			X	X	X
Caregiver Adherence to CGMI-V Survey (Satisfaction Survey)				X	X
Change in status survey (CG/CR)				X	X

6.2 Description of Evaluations

Study evaluations consist of: (1) eligibility screening for inclusion criteria, (2) Baseline assessment immediately after enrollment, (3) 8-weeks post-baseline, for intervention effects, and (4) 24-weeks post-baseline for maintenance effects.

6.2.1 Screening Evaluation

Consenting Procedure

The Project Director will schedule a phone or online screening interview with caregivers expressing an interest in the study. The Project Director will explain the screening process and the questionnaires used to ascertain participant eligibility and invite any caregiver questions. After all questions are addressed, verbal consent to screening will be documented after the screener explicitly asks the caregivers if they consent.

Screening

Caregivers who verbally consent will be screened using computer-assisted telephone interviewing (CATI) for the following inclusion criteria:

- 21 years of age or older
- Identified as family member, fictive kin (self-identified family member) or partner of care recipient
- Within the first two years of care recipient's permanent placement in a long-term care facility (LTCF)
- Care recipient is a resident in a dementia or memory care unit in the LTCF, where a diagnosis of ADRD is mandatory
- Possessing self-reported basic computer literacy and in-home internet access
- Able to speak, read, and write English
- Not currently attending another ADRD caregiver grief management group
- Experiencing high to moderate levels of grief per screening with the Marwit-Meuser Caregiver Grief Inventory-Short Form³⁸ (scores 25 or above), and/or experiencing high levels of depressive symptoms per screening with PHQ9³⁹ (scores 10 or above)

Caregivers meeting all eligibility criteria will be sent a consent form including detailed information about the study. A phone or online meeting will be scheduled with the PI or the Project Director within the next 24-48 hours for discussion of study,

content of consent form, and to respond to any other questions.

Enrollment

Participants will be enrolled into the study once their signed study informed consents are being returned to study office. A baseline appointment will be scheduled within the next 24-48 hours.

Baseline Assessments

Participants who are enrolled into the study, will be assessed at baseline using CATI, for the following outcomes:

- Caregiver and care recipient socio demographics
- Caregiver and care recipient situational characteristics
- Caregiver grief
- Caregiver depressive symptoms
- Caregiver anxiety symptoms
- Caregiver positive states of mind
- Caregiver conflict with facility staff
- Caregiver satisfaction with care in the facility
- Caregiver knowledge of ADRD
- Caregiver sense of loss
- Caregiver guilt
- Caregiver role captivity

Randomization

The study will be implemented in six waves. Beginning in Month 5 of the study, we will start recruiting and enrolling 24 caregivers for Wave 1, who will be randomly assigned to either the CGMI-V condition ($n = 12$; 6/group) or MT control condition ($n = 12$). After these 24 caregivers have been enrolled, the study team will start recruiting and enrolling an additional 24 caregivers for Wave 2. There will be a total of six waves. Each wave will have 8 weeks to recruit, screen, enroll, randomize to condition, and complete baseline data collection, followed by CGMI-V implementation over 8 consecutive weeks (Figure 1).

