Control condition. Caregivers in the control condition will receive Minimal Treatment (MT) consisting of written information about late-stage ADRD (Alzheimer's Association) at baseline. The Project Director will mail caregivers in the MT control condition all written information materials.

4 **SELECTION AND ENROLLMENT OF PARTICIPANTS**

We will recruit a sample of 144 ADRD caregivers who have a family member residing in dementia care or memory care units in long-term care facilities located in the Chicago metropolitan area. We have well-established collaborating relationships with 35 long-term care facilities that will give us access to a diverse pool of approximately 1,000 ADRD family caregivers.

4.1 **Inclusion Criteria**

Participants must meet all inclusion criteria listed below in order to participate in this study.

- 21 years of age or older
- Identified as family member, fictive kin (self-identified family member) or partner of care recipient at any time post permanent placement of care in LTCF
- Care recipient has a documented ADRD diagnosis and resides in any type of unit in a long-term care facility
- Possessing self-reported basic computer literacy and in-home internet access
- Able to speak, read, and write English
- Not currently attending another ADRD caregiver grief management group

- Experiencing high to moderate levels of grief per screening with the Marwit-Meuser Caregiver Grief Inventory-Short Form (scores 25 or above), and/or experiencing high levels of depressive symptoms per screening with PHQ9 (scores 10 or above)
- Caregivers whose care recipients die during the course of the intervention will remain in the study

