9.2.1 Treatment Assignment Procedures

The study is a Stage I longitudinal randomized clinical trial. ADRD caregivers whose family members are in LCTFs will be recruited, screened for inclusion criteria, and randomly assigned to either CGMI-V or a Minimal Treatment (MT) control condition. Randomization will be stratified in six Waves of 24 participants each, to insure that there are exactly 12 participants in each condition. In Wave 1, we will randomly assign the first 24 enrolled participants to either the CGMI-V condition ($n = 12$; 6/group) or MT control condition ($n = 12$). The same process will continue for the next five Waves. Recruiters and data collectors will be blinded as to the random assignment of each participant. Once caregivers sign the consent to enroll in the study, the Project Director will use randomization software to assign each enrolled participant to CGMI-V or the MT condition. The Project Director will then inform the participants directly of their assignments and ask them to maintain confidentiality about their assignment at data collection points.

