9.5 Data Analyses

We will track all study participants following CONSORT guidelines and enter all data into a REDCap database. SPSS for Windows (Version 22) and R (Version 3.1.1) will be used for data management and statistical analysis. A two-tailed 0.05 significance level will be used for all statistical tests except where noted below. All analyses will be performed on an intent-to-treat basis. Missing data will be imputed using the R mi package, a multiple imputation computer program based on the work of Rubin.

Histograms will be obtained for these variables, and skew and kurtosis will be assessed to assess statistical normality. From previous research, we expect the error rates to have statistically normal distributions or distributions that can be transformed to normality using logarithmic and square root transformations. We will perform any necessary transformations using Tukey's ladder of transformation before conducting statistical analysis. Because these trials are designed to estimate precise effect sizes rather than probability values, the results of each trial will be the effect size (comparing treatment and control groups) and confidence intervals around this estimate.

Aim 1. Controlling for background variables, establish effect sizes of the CGMI-V condition and Minimal Treatment (MT) control condition on changes in a primary caregiver chronic grief outcome.

Multilevel linear models will be run for the CGMI-V and MT control conditions. Multilevel models are used to estimate autocorrelation across the three time points. We hypothesize that chronic grief will decrease more in the CGMI-V condition relative to the MT control condition. Caregiver sex, age, relationship to the care-receiver, as well as care recipient death or discharge from the facility, will be controlled for as covariates in the analysis. Sex and caregiver/care recipient relationship, as well as care recipient death or discharge from the facility, will be entered into the model as dummy-coded variables. We will examine the interaction effects (δ) to make certain that they are large

enough to justify a more robust clinical trial. While there is some likelihood of obtaining significant findings in this study, the primary purpose of this analysis is to estimate effect sizes.

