10 DATA COLLECTION AND QUALITY ASSURANCE

10.1 Data Collection Forms

Trained Research Assistants (RAs) blinded to treatment condition will use Computer-assisted Telephone Interviewing (CATI) to complete all initial screening and data collection interviews. Study RAs will read each question and enter the response directly into the secure, web-based Research Electronic Data Capture (REDCap).

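### The screening grief and PHQ-9 totals precede allocation on every reading of the protocol, yet section 9.5 gives them no role in the outcome models or the imputation

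*Combined protocol and SAP*

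**What the plan says.** Two instruments are given at eligibility screening: the MM-CGI Short Form ("Experiencing high to moderate levels of grief per screening with the Marwit-Meuser Caregiver Grief Inventory-Short Form", 25 or above) and, joined by and/or, the PHQ-9 ("experiencing high levels of depressive symptoms per screening with PHQ9", 10 or above); see 4.1 and 6.2.1. Section 10.1 covers screening as well as outcome interviews and has research assistants "enter the response directly into the secure, web-based Research Electronic Data Capture (REDCap").

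For Aim 1, and by reference Aims 2 and 3, section 9.5 states: "Caregiver sex, age, relationship to the care-receiver, as well as care recipient death or discharge from the facility, will be controlled for as covariates". Baseline grief enters as one of the repeated measures: "Multilevel models are used to estimate autocorrelation across the three time points". The quantity of interest is an interaction: "We will examine the interaction effects". On incomplete data, 9.5 promises intent-to-treat analysis and says "Missing data will be imputed using the R mi package", without listing the variables in the imputation model.

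On timing, 9.2.1 says: "Once caregivers sign the consent to enroll in the study, the Project Director will use randomization software to assign each enrolled participant". The schedule in 6.1 has an enrolment/randomization column ahead of baseline, and it first collects socio-demographics and the outcome scales at baseline. Sections 3 and 6.2.1 list randomizing before baseline data collection within each wave. Against this, 6.2.1 describes the baseline assessments before its randomization paragraph, and the wave steps in 4.3 leave randomizing out of the list.

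**The concern.** Section 9.5 says the trial's result is an effect size with its confidence interval, so prognostic information already collected has direct value. The screening totals measure grief and depression, and knowledge of the arm cannot have altered them. The same cannot be said of the baseline interview if allocation comes first, because under 9.2.1 the Project Director tells participants their assignment directly.

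The order also matters for missing data. If a caregiver is allocated and then lost before the baseline interview, intent to treat still counts that person. The outcome scales and socio-demographics would all be absent. An imputation model without the screening totals would then have essentially nothing about that person's grief or depression.

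**Working it through.** **The plan's own figure (9.2).** SD 35.78, 64 per arm: 35.78/√64 = 4.47; × 1.96 = 8.77 units; 8.77/35.78 = 0.245 SD; 64/0.9 = 71.1, rounded up to 72. This reproduces, but only as the precision of one arm's mean. For the difference between arms, 35.78 × √(2/64) = 6.33; × 1.96 = **12.40** units (0.35 SD). The half-widths below start from 12.40, assume 64 complete cases per arm and the same SD at each occasion, and ignore clustering within video groups.

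**Correlations.** Section 9.1 gives MM-CGI stability of .71 to .75, reported for the subscales; using it for the total is an assumption. Every correlation involving the screening score is also an assumption.

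**1. Gain beyond a baseline covariate.** Half-width = 12.40 × √(1 − R²). With b = baseline, s = screening, y = follow-up:

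R² = (r_by² + r_sy² − 2·r_by·r_sy·r_sb)/(1 − r_sb²).

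- *Screening acts only through baseline* (r_sy = r_by × r_sb): no gain. At r_by = .71, half-width 8.73 before and after.
- *r_by = .71, r_sb = .80, r_sy from .568 to .71*: 8.73 falls to between 8.73 and 8.22 (0-5.8%).
- *Stable level plus independent noise, r_by = .73*: baseline only, 12.40 × √(1 − .533) = 8.47. With an assumed short-form reliability of .50, residual variance is .425 and half-width 8.08 (4.6% narrower). With .73, they are .384 and 7.68 (9.3%).
- *Extreme corner, r_by = r_sy = .75, r_sb = .70*: 8.20 falls to 7.21 (12%). This needs the screening score to track follow-up more closely than it tracks baseline, so it is not a planning value.

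**2. Gain inside the planned group-by-time model.** The unconstrained interaction has half-width 12.40 × √(2(1 − r)).

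- *r = .71*: 9.44. Adding the screening score as a main effect leaves it at 9.44 (algebra and 40 simulated fits). If screening acts through baseline with r_sb = .80, score-by-time terms bring it to about 9.0-9.2. Baseline MM-CGI as a covariate gives 8.73.
- *Stable-level model, r = .73*: 12.40 × √.54 = 9.11. Screening is equally correlated with baseline and follow-up, so it does not predict change, and score-by-time terms leave 9.11.

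The gains in step 1 therefore need baseline to be a covariate as well, or a common pre-intervention mean across arms.

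**3. Screening as the only usable pre-allocation covariate.** 12.40 × √(1 − r²): 11.36 at r = .4 and 8.85 at r = .7, which is 8% to 29% narrower than an unadjusted follow-up comparison. It matches the 9.44 of the planned interaction only when 1 − r² = .58, that is r ≈ .65. Below that the argument is protection from knowledge of the arm, not width.

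**4. Early losses.** In the stable-level model the share of follow-up variance predictable from screening alone is .73 × .50 = .365 to .73 × .73 = .533, per person affected. If a fraction m of an arm lacks the outcome, the variance of the arm mean falls by about m·r². For r = .5 to .8:

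- m = 2% (1.4 of 72): 0.5-1.3%
- m = 5% (3.6 of 72): 1.2-3.2%
- m = 10% (7.2 of 72): 2.5-6.4%

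No corresponding calculation was made for depression or anxiety, because the documents give no correlation with the PHQ-9.

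**The case against.** The strongest reply is that the plan already models a full 50-item baseline grief score, so a shorter earlier version adds little. That largely stands: the gain can be zero, and selecting caregivers on these scores restricts their range and weakens their correlation with follow-up. Making better use of the baseline score is worth more in the planned model (9.44 to 8.73).

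Four further points also stand:

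- A reader might infer that 9.5 excludes the screening scores from imputation. It does not. It lists no imputation variables, and the data are in REDCap.
- A reader might infer that the scores serve only as entry cut-offs. The PHQ-9 suicidality item is also a safety parameter (7.1). Read literally, 7.2 has the 7.1 parameters, including a CES-D score, assessed at pre-enrolment screening too; the schedule in 6.1 does not show that.
- The and/or gate does not guarantee that every enrolled caregiver completed both instruments.
- The early-loss problem exists only if allocation precedes baseline. Even then the number may be small: the baseline appointment is scheduled within 24-48 hours of enrolment, the 10% allowance covers all attrition, and caregivers who drop out are to be invited to both follow-ups.

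None of this gives the scores a stated role or settles the order of baseline and allocation.

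**Conclusion.** The point holds as an inexpensive improvement, not as an error that biases the planned estimate. The two screening totals have no stated analytic role, and the documents place them before allocation on every reading.

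Beyond a usable baseline covariate, expect an interval about 0-10% narrower. As the sole pre-allocation covariate, expect about 8-29% narrower than unadjusted, for assumed r of .4 to .7. For early losses the benefit is mainly a more credible missing-at-random assumption.

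A reader might infer that the plan forfeits a definite amount of precision, or that adding the score to the model as written would recover it. The documents support neither: the upper figures rest on a stable-level model and a short-form reliability they do not give, and a main effect in the unconstrained interaction model changes nothing. Nor do they show that many caregivers would be lost before baseline; no number is given.

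**What to change.** 1. **Imputation (9.5).** Keep both screening totals in the analysis dataset and name them as auxiliary variables in the imputation model, with arm, wave and all outcome occasions.
2. **Aims 1-3 (9.5).** Model the 8- and 24-week scores with the baseline outcome and the matching screening score as covariates: MM-CGI Short Form for grief, PHQ-9 for depression and anxiety. Alternatively, give both pre-intervention occasions a common mean across arms. The other secondary outcomes have no matching screening score and would use baseline alone. If baseline may follow disclosure of the arm, use the screening score as the pre-allocation covariate.
3. **Order of events.** Reconcile 4.3, 6.1, 6.2.1 and 9.2.1 on whether baseline or allocation comes first, and report losses between the two by arm.

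The cost is SAP wording and a few model degrees of freedom, with no new data collection. The consent form should cover use of enrolled caregivers' screening answers.
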